9.2.1 Non-inferiority test of platinum

9.2.1.1 Sample Size and Accrual

Based on the review (by Von Minckwicz et al.(5)) of patients with TNBC (basal-like and non-basal-like) that do not achieve a pCR after neoadjuvant chemotherapy, the outcome contingent on tumor size in the residual disease show no difference between patients with pT1 and pT2; i.e. 50% of those patients recur in ~ 60 months. Of note, that would support the reasoning behind allowing patients with residual tumors ≥ 1 cm. The ones with pT3 and pT4 mimic the cohort of patients with basal-like TNBC in the analysis by Balko et al.(8) ; where 50% of them recur in 18 months. The patients with pT3 and pT4 represented ~ 20% of the

whole number of patients (in the review by Von Minckwicz et al.(5)) that did not achieve a pCR. We would expect that 20% of the patients that would potentially be accrued in our current trial would have a median IDFS of ~ 18 months and 80% would have a median DFS of ~60 months. Therefore, it would be reasonable to assume that a conservative estimate of the actual median DFS would be 48 months (i.e., 4-year DFS rate of 50%) for the study patients if receiving no chemotherapy after surgery, with a median OS of 60 months (i.e., 5-year OS rate of 50%). Based on the CREATE-X trial, the 4-year DFS rate was 67% in the 296 TNBC patients when receiving capecitabine (HR=0.58, 95% CI 0.39 – 0.87). Therefore, a conservative estimate of the 4-year IDFS rate would be 67% ($0.5^{0.58}=0.67$) for the capecitabine arm in patients with basal-like TNBC disease in this trial.

The null hypothesis for testing non-inferiority of platinum is defined as that the hazard ratio (HR) for platinum/capecitabine ≥ 1.154 (i.e., HR of 1.154 is used as the non-inferiority margin). This corresponds to a 4-year IDFS rate of $\leq 63\%$ on platinum if the 4-year IDFS rate is 67% on capecitabine arm. With a total accrual of 562 patients (281 on each arm) and full information of 196 IDFS events, this non-inferiority test would have about 83% power, with a one-sided 0.025 significance level, to reject the null hypothesis of inferiority of platinum under the alternative hypothesis of HR=0.754 for platinum/capecitabine, i.e., the 4-year IDFS rate for platinum is expected to be 73.9%.

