9.2.1.2 Interim analysis plan

The study will be monitored by the ECOG-ACRIN Data and Safety Monitoring Committee (DSMC) according to the principals of group-sequential methods. The first interim analysis will be performed at the first DSMC meeting when

Rev. Add7

at least 25% of the total information has been reported. Since 196 IDFS failures are required as the total information under the alternative hypothesis, the first interim analysis is estimated to take place after 49 IDFS failures have occurred, which corresponds to 2.9 years after activation of the study in calendar time, under the accrual and failure rate assumptions mentioned above. Interim analysis will be performed for each subsequent DSMC meeting until either the criteria for early stopping (described below) are met or the total planned number of IDFS failures has been reported. In total, this design is expected to incorporate 8 interim analyses and one final analysis for IDFS comparisons.

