Table 1: Expected timing of interim analyses and critical values under the alternative hypothesis of HR=0.754 (i.e., 4-year IDFS rate of 67% on capecitabine vs. 73.9% on platinum)

| Repeated analysis | Time from study activation (years) | Information time (%) | Number of Failures under alternative | Upper boundary (critical value for two-sided 95% RCIs) |
|-------------------|------------------------------------|----------------------|--------------------------------------|--|
| 1 | 2.9 | 0.25 | 49 | 3.2905 |
| 2 | 3.4 | 0.34 | 67 | 3.2905 |
| 3 | 3.9 | 0.44 | 87 | 3.2905 |
| 4 | 4.4 | 0.55 | 107 | 2.9084 |
| 5 | 4.9 | 0.65 | 126 | 2.6218 |
| 6 | 5.4 | 0.74 | 145 | 2.4376 |
| 7 | 5.9 | 0.83 | 162 | 2.2980 |
| 8 | 6.4 | 0.92 | 179 | 2.1870 |
| Final | 6.9 | 1.00 | 196 | 2.0962 |

In addition to efficacy monitoring for the non-inferiority test, the trial will be monitored to allow early stopping for inferiority of platinum based on conditional power and the above RCI methods. At each interim analysis, the conditional power of the log rank test for the primary comparison at a one-sided type I error rate of 0.025 will be computed using simulation, and if the conditional power of the assigned treatment analysis is < 10% and the lower boundary of the above two-sided 95% RCI is greater than 0.754 for arm B/arm C (the alternative hypothesis), then the trial would be stopped due to futility unless there is other supporting evidence for non-inferiority of platinum at the time. We would conclude that the trial fail to reject the null hypothesis of inferiority of platinum, and platinum is inferior to capecitabine. If the conditional power is > 10% or the lower boundary of the 95% RCI is below 0.754, the trial would continue.

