9.2.2 Superiority test of platinum

If inferiority of platinum is rejected at an interim analysis or the final analysis, the primary hypothesis is answered, and a superiority test of platinum (i.e., the secondary hypothesis) is then performed at an overall one-sided type I error rate of 0.025, using the same RCIs used for the above non-inferiority test. For the superiority test, the null hypothesis is that HR=1 for platinum/capecitabine. Assuming the alternative hypothesis is HR=0.653 for platinum/capecitabine for the superiority test, with 562 basal-like TNBC patients and total information of 196 IDFS events, there would be at least 82% power to detect a 34.7% reduction in the IDFS failure hazard rate using stratified log rank test with an overall one-sided type I error rate of 0.025, if the trial continues regardless of the results of non-inferiority test. This reduction in IDFS failure hazard rate corresponds to an

Rev. Add7

improvement in 4-year IDFS rate from 67% on the capecitabine arm^{5,38} to 77% on the platinum arm, under the assumption of exponential distribution of IDFS.

At any interim analysis or the final analysis, when the upper confidence limit for the HR is less than 1, the null hypothesis of no difference between the two arms would be rejected and we would conclude that platinum is superior to capecitabine in improving IDFS in patients with basal-like TNBC. If this occurs at an interim analysis, DSMC may consider stopping the trial early for efficacy. If the RCI for the HR does not include the target alternative HR of 0.653 for platinum/capecitabine, the study may be stopped early for lack of benefit (i.e., fail to reject the null hypothesis for the superiority test of platinum).

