In summary, if, at any of the interim analyses, the null hypotheses for both non-inferiority test of platinum (i.e., $HR \geq 1.154$) and superiority test of platinum (i.e., $HR=1$) are rejected, the DSMC may consider stopping the trial early. If only the inferiority of platinum is rejected and the superiority test of platinum dose not cross the stopping boundary, the trial will continue. In this case, RCIs would be computed using the same upper boundary listed in Table 1, but the stopping rules would be shifted to the equality vs. superiority difference. If criteria for early stopping (either for efficacy or for futility) are not met for the non-inferiority test, the final analysis for the non-inferiority test will be performed when IDFS event has occurred in 196 patients. If inferiority of platinum is rejected at the final analysis, superiority test would then be performed at the final analysis.

For the IDFS endpoint, the primary analysis will compare treatment groups defined by the randomized treatment assignment (intent-to-treat analysis, ITT). A secondary analysis will be performed comparing groups defined by treatment received. The results will be creditable only if the two analyses are reasonably consistent.

Although one-sided type I error rate of 0.025 is used for hypothesis test in the study design, two-sided 95% RCIs will be used in the DSMC and final reports for reporting purpose.

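### A futility stop is pre-specified to mean that platinum is inferior, but the stopping rule cannot show this

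*Combined protocol and SAP*

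**What the plan says.** The primary test is of non-inferiority. Section 9.2.1.1 states that "HR of 1.154 is used as the non-inferiority margin", so the null hypothesis is HR ≥ 1.154. The trial is sized "to reject the null hypothesis of inferiority of platinum under the alternative hypothesis of HR=0.754 for platinum/capecitabine". Non-inferiority is concluded when the upper RCI limit falls below 1.154.

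The paragraph after Table 1 in Section 9.2.1.2 adds a second rule: "the trial will be monitored to allow early stopping for inferiority of platinum based on conditional power and the above RCI methods". The trial stops when conditional power is under 10% and the lower limit of the two-sided 95% RCI is above 0.754, "unless there is other supporting evidence for non-inferiority of platinum at the time". The paragraph calls this a futility stop and then gives the conclusion: "We would conclude that the trial fail to reject the null hypothesis of inferiority of platinum, and platinum is inferior to capecitabine".

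Section 9.2.2 has a parallel lack-of-benefit rule for the superiority test. It ends at "fail to reject the null hypothesis for the superiority test of platinum" and claims nothing more.

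**The concern.** Failing to reject HR ≥ 1.154 is not evidence that HR ≥ 1.154. The other positive conclusions in the design are tied to an RCI limit: non-inferiority needs an upper limit below 1.154, and superiority an upper limit below 1. Inferiority has no such criterion. Nothing in the plan requires the lower limit to exceed 1 or 1.154 before platinum is called inferior, and no test of inferiority is specified.

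This is the pre-specified reading of the primary endpoint after a futility stop in a phase III trial meant to change practice. Not shown to be non-inferior and shown to be inferior are different messages. The one-sided 0.025 error rate covers a false claim of non-inferiority, not a false claim of inferiority.

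**Working it through.** **Inputs.** Margin 1.154, alternative 0.754, 196 events and one-sided 0.025 (Section 9.2.1.1). Events d and critical values c by look (Table 1). Conditional power is computed at HR 0.754 (the list of design changes that opens Section 9). The number of looks follows the plan: "this design is expected to incorporate 8 interim analyses and one final analysis for IDFS comparisons". With 1:1 allocation, SE(log HR) = 2/√d and information I = d/4.

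**Reproducing the design.** √(196/4) × ln(1.154/0.754) = 7 × 0.4256 = 2.979. Power is Φ(2.979 − 1.960) = 84.6% for a fixed test and Φ(2.979 − 2.0962) = 81.1% using the final critical value alone. Simulating all nine looks gives 83.1% power at HR 0.754 and 2.5% error at HR 1.154. The stated power of about 83% reproduces.

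**Stopping thresholds.**
- RCI condition: observed HR > 0.754 × exp(2c/√d).
- Conditional power condition, with I_f = 49: log HR > [49 ln 1.154 − 2.0962 × 7 − ln 0.754 × (49 − I) + 1.2816 √(49 − I)] / I.

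At look 8 (d = 179, I = 44.75), the RCI condition gives 0.754 × exp(2 × 2.1870/√179) = 0.754 × 1.387 = 1.046. The conditional power condition gives (7.018 − 14.673 + 1.200 + 2.642)/44.75 = −0.085, an HR of 0.918. Both must hold, so the threshold is the larger.

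| Look | Events | RCI condition | Cond. power condition | Smallest HR that stops | RCI at that HR | HR needed for lower limit > 1 | HR needed for lower limit > 1.154 |
|---|---|---|---|---|---|---|---|
| 1 | 49 | 1.931 | 2.355 | 2.355 | 0.920–6.029 | 2.560 | 2.955 |
| 2 | 67 | 1.685 | 1.684 | 1.685 | 0.754–3.765 | 2.234 | 2.579 |
| 3 | 87 | 1.527 | 1.363 | 1.527 | 0.754–3.092 | 2.025 | 2.337 |
| 4 | 107 | 1.323 | 1.191 | 1.323 | 0.754–2.322 | 1.755 | 2.025 |
| 5 | 126 | 1.203 | 1.088 | 1.203 | 0.754–1.919 | 1.595 | 1.841 |
| 6 | 145 | 1.130 | 1.014 | 1.130 | 0.754–1.694 | 1.499 | 1.730 |
| 7 | 162 | 1.082 | 0.963 | 1.082 | 0.754–1.552 | 1.435 | 1.656 |
| 8 | 179 | 1.046 | 0.918 | 1.046 | 0.754–1.450 | 1.387 | 1.600 |

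At every look the RCI at the stopping threshold contains both 1 and 1.154. At looks 6 to 8 the point estimate itself can lie inside the margin.

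**How often.** These are simulated probabilities of a futility stop with all eight interims and no override. Paths that had already met non-inferiority cannot stop.

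| True HR | 0.754 | 0.85 | 0.90 | 0.95 | 1.00 | 1.154 |
|---|---|---|---|---|---|---|
| Futility stop | 1.9% | 10% | 18% | 29% | 41% | 77% |

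Among stops at true HR 1.00, the median observed HR is 1.18 and 43% of observed HRs are below 1.154. The RCI contains 1 in 99.8% and lies wholly above 1.154 in 0.02%. Even an unadjusted 95% interval excludes 1 in only about 10%. Among stops at true HR 1.154, the lower RCI limit exceeds 1 in 0.6%. At true HR 1.30, the RCI lies wholly above 1.154 in only 0.26%.

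**Sensitivity at true HR 1.00.**
- Override used once: 31%. Used twice: 22%.
- Fewer interims with re-derived boundaries: 18% (two, at 1/3 and 2/3 information), 26% (two at 50/75%, or three at 25/50/75%), 33% (Table 1 looks 1, 3, 5, 7) and 42% (looks 2, 4, 6, 8).
- Using 1.96 instead of 2.0962 in the conditional power calculation moves only the thresholds at looks 1 and 2 (to 2.545 and 1.783) and leaves the 41% unchanged.

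**The case against.** The strongest reply is that this is loose drafting with no operating consequence. Inferiority is the plan's own name for its null, so the clause may mean only that the null is retained, which the same sentence has already said correctly. Every stop needs an observed HR above 1. At true HR 1.00, 57% of stops have an observed HR above the margin, and at a true HR of 1.154 the rule stops 77% of trials, so the evidence does lean against platinum.

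There are also safeguards. The override clause can keep the trial going. Section 9.2.2 says "two-sided 95% RCIs will be used in the DSMC and final reports for reporting purpose", so an interval containing 1 would be visible. It also makes the IDFS result depend on reasonable agreement between the intent-to-treat and treatment-received analyses. Finally, the 41% is a property of the stopping rule, assumes full adherence to Table 1, and would be the same after rewording.

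Most of this stands as a limit on the harm. The 41% measures how often the sentence would apply, not how often a report would mislead, and the documents do not allow the latter to be estimated. None of it makes the clause correct. Read as the plan's null, inferiority would need an RCI above 1.154, which almost never occurs at a stop. A point estimate leaning one way is not a demonstration. The override governs whether to stop, not what to conclude afterwards. Reporting the RCI would expose the contradiction, not remove it.

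**Conclusion.** The concern holds. The second half of the sentence is unsupported whenever the rule is met without an RCI that also excludes 1 (or 1.154), which is nearly always. That conclusion depends only on the logic of the test and the Table 1 thresholds. The frequency with which the sentence would apply, about 41% at true HR 1.00 and 18% at true HR 0.90, rests on the normal approximation, the Table 1 event counts and no override. Across the other looks and override patterns examined, the figure at true HR 1.00 runs from 18% to 42%.

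This should be fixed before any interim result is reported. It does not affect the non-inferiority error rate, power, stopping boundary or trial conduct.

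**What to change.** In the paragraph after Table 1 in Section 9.2.1.2:
- Delete the clause declaring platinum inferior. State instead that non-inferiority of platinum was not established, and that the HR will be reported with its RCI.
- Describe the rule as early stopping for futility where it is introduced, matching the rest of that paragraph and the opening of Section 9.

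If the sponsor wants to be able to claim inferiority, that claim needs its own pre-specified criterion, for example a lower RCI limit above 1.0. This is optional and not needed to cure the defect.

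The cost is one clause and one label. Boundaries, sample size, power and conduct stay as they are. The only loss is a weaker statement after a futility stop.

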9.2.2 Superiority test of platinum

If inferiority of platinum is rejected at an interim analysis or the final analysis, the primary hypothesis is answered, and a superiority test of platinum (i.e., the secondary hypothesis) is then performed at an overall one-sided type I error rate of 0.025, using the same RCIs used for the above non-inferiority test. For the superiority test, the null hypothesis is that HR=1 for platinum/capecitabine. Assuming the alternative hypothesis is HR=0.653 for platinum/capecitabine for the superiority test, with 562 basal-like TNBC patients and total information of 196 IDFS events, there would be at least 82% power to detect a 34.7% reduction in the IDFS failure hazard rate using stratified log rank test with an overall one-sided type I error rate of 0.025, if the trial continues regardless of the results of non-inferiority test. This reduction in IDFS failure hazard rate corresponds to an

Rev. Add7

improvement in 4-year IDFS rate from 67% on the capecitabine arm^{5,38} to 77% on the platinum arm, under the assumption of exponential distribution of IDFS.

At any interim analysis or the final analysis, when the upper confidence limit for the HR is less than 1, the null hypothesis of no difference between the two arms would be rejected and we would conclude that platinum is superior to capecitabine in improving IDFS in patients with basal-like TNBC. If this occurs at an interim analysis, DSMC may consider stopping the trial early for efficacy. If the RCI for the HR does not include the target alternative HR of 0.653 for platinum/capecitabine, the study may be stopped early for lack of benefit (i.e., fail to reject the null hypothesis for the superiority test of platinum).

In summary, if, at any of the interim analyses, the null hypotheses for both non-inferiority test of platinum (i.e., $HR \geq 1.154$) and superiority test of platinum (i.e., $HR=1$) are rejected, the DSMC may consider stopping the trial early. If only the inferiority of platinum is rejected and the superiority test of platinum dose not cross the stopping boundary, the trial will continue. In this case, RCIs would be computed using the same upper boundary listed in Table 1, but the stopping rules would be shifted to the equality vs. superiority difference. If criteria for early stopping (either for efficacy or for futility) are not met for the non-inferiority test, the final analysis for the non-inferiority test will be performed when IDFS event has occurred in 196 patients. If inferiority of platinum is rejected at the final analysis, superiority test would then be performed at the final analysis.

For the IDFS endpoint, the primary analysis will compare treatment groups defined by the randomized treatment assignment (intent-to-treat analysis, ITT). A secondary analysis will be performed comparing groups defined by treatment received. The results will be creditable only if the two analyses are reasonably consistent.

Although one-sided type I error rate of 0.025 is used for hypothesis test in the study design, two-sided 95% RCIs will be used in the DSMC and final reports for reporting purpose.

9.3 Secondary Endpoints

9.3.1 Overall Survival

Overall survival (OS) is an important secondary endpoint in the study, and only superiority test of platinum is planned for OS. With a total accrual of 562 basal-like patients, total information of 240 deaths is needed to give about 80% power to detect a 30% reduction (i.e., $HR=0.7$ for platinum/ capecitabine under alternative hypothesis) in the OS failure hazard rate using stratified log-rank test with one-sided type I error rate of 0.025, without any interim analysis plan. This reduction in OS failure hazard rate corresponds to an improvement in 5-year OS from 66% on capecitabine arm to 75% on platinum arm, under the assumption of exponential distribution of OS. The final analysis for OS is expected to occur at about 10.5 years after study activation (3.9 years of accrual + 6.1 years of follow up+0.5 years of

data collection and cleaning, i.e., 3 years after IDFS final analysis) to reach the expected number of OS failures. The OS comparison will be intent-to-treat analysis of all randomized patients regardless of eligibility status. A secondary analysis of OS will be conducted in eligible patients.

9.3.2 Toxicity

Another secondary endpoint of the study is to evaluate toxicities in patients with basal-like TNBC. All patients who start protocol therapy (i.e., receive at least one dose of protocol treatment) will be included in toxicity analysis. Assuming 14 basal-like TNBC patients (14/281=5%) will not start protocol therapy in each arm, with 267 evaluable patients, the binomial exact 95% confidence interval for toxicity rate would be no wider than 0.12, and there would be at least 83% power to detect a 13% difference in grades 3 or higher toxicity rate, using Fisher exact test with one-sided type I error rate of 0.025. For each individual platinum agent (carboplatin or cisplatin), the binomial exact 95% confidence interval for toxicity rate would be no wider than 0.17 if about the same number of patients (n=133) take each agent.

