2.2 Secondary Clinical Objectives

- 2.2.1 To evaluate OS and RFS in the two arms in patients with TNBC with residual basal-like disease after neoadjuvant chemotherapy.
- 2.2.2 To characterize the side effects and tolerability of each platinum agent (cisplatin and carboplatin) as well as capecitabine in patients with TNBC with residual disease after neoadjuvant chemotherapy.
- 2.2.3 To identify the rate of basal-like gene expression using PAM50 analysis by digital mRNA quantitation amongst drug-resistant residual TNBC after neoadjuvant chemotherapy.
- 2.2.4 To compare the IDFS in TNBC patients with residual non-basal-like disease after neoadjuvant chemotherapy who are randomized to post-preoperative platinum-based chemotherapy with those who are randomized to capecitabine (exploratory analysis).
- 2.2.5 To assess the difference in health-related quality of life (HRQL) between the platinum based and capecitabine chemotherapy arms.
- 2.2.6 To describe the rate of neurotoxicity over time in the platinum arm, the rate of medication adherence in the capecitabine arm and the rates of amenorrhea in both arms (exploratory).

Rev. Add7

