Toxicity analysis will be conducted in all basal-like TNBC cases receiving at least one dose of chemotherapy (i.e., all treated population). Adverse events will be graded using the National Cancer Institute (NCI) Common Terminology Criteria for Adverse Events (CTCAE) version 4.0. All treatment-emergent and baseline adverse events and hematological/biochemical toxicities based on laboratory measurements will be summarized for patients on each arm. The incidence of deaths and treatment-emergent serious adverse events will be calculated along with exact 95% CI based on binomial distribution and compared between treatment arms using Fisher exact test. Also, the incidence of adverse events leading to discontinuation of chemotherapy and/or withdrawal from the study will be summarized and listed. Toxicity in all patients (including both basal-like and non-basal like patients) will be summarized and compared between treatment arms as well.

The proportion of basal-like TNBC in all screened TNBC patients will be calculated with exact 95% CI based on binomial distribution.

Rev. Add6

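### The main toxicity set is limited to basal-like patients although objective 2.2.2 is not, and the per-agent exact interval width of 0.17 should read 0.18

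*Combined protocol and SAP*

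**What the plan says.** Objective 2.2.2 is: "To characterize the side effects and tolerability of each platinum agent (cisplatin and carboplatin) as well as capecitabine in patients with TNBC", continuing to residual disease after neoadjuvant chemotherapy. It sets no subtype limit, whereas the neighbouring objectives 2.2.1 and 2.2.4 name basal-like or non-basal-like disease.

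Section 9.3.2 narrows this: "Another secondary endpoint of the study is to evaluate toxicities in patients with basal-like TNBC". Its next sentence is broad again: "All patients who start protocol therapy (i.e., receive at least one dose of protocol treatment) will be included in toxicity analysis". The sizing that follows uses basal-like patients only, 281 per arm less 14 non-starters. It states that "with 267 evaluable patients, the binomial exact 95% confidence interval for toxicity rate would be no wider than 0.12" and, for each platinum agent at n=133, that "the binomial exact 95% confidence interval for toxicity rate would be no wider than 0.17". It also claims at least 83% power for a 13-point difference by a one-sided 0.025 Fisher exact test.

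Section 9.4 lists the secondary endpoint as toxicity in basal-like TNBC and then says: "Toxicity analysis will be conducted in all basal-like TNBC cases receiving at least one dose of chemotherapy (i.e., all treated population". The same paragraph later adds: "Toxicity in all patients (including both basal-like and non-basal like patients) will be summarized and compared between treatment arms as well".

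The Amendment #7 summary at the start of Section 9 says that subtype is now determined after randomization. About 7% of patients are expected to have assay failure; they are still randomized and are to be analysed separately as an exploratory objective. For that group Section 9.4 specifies only IDFS, OS and RFS.

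**The concern.** The objective and the analysis sections describe different populations, and the label attached to the basal-like set in Section 9.4 does not describe it. Two programmers working from these sections could build different safety sets.

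The basal-like focus is justified in Section 9.2 by where platinum benefit is expected. No reason is given why toxicity of these drugs would depend on tumor subtype, so for safety the restriction costs precision with no stated gain. The comparison matters because Section 9.2 gives lower toxicity of platinum as one of its two reasons for the non-inferiority design. The gap is clearest for patients with a failed assay, who are treated like everyone else but are not expressly placed in any toxicity set, and for the individual platinum agents, which objective 2.2.2 names.

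The per-agent width is a smaller, separate matter: a bound attributed to the exact method that this method does not meet.

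**Working it through.** **Inputs.** Section 9.3.2: 267 evaluable per arm, 133 per platinum agent, 5% non-starters, stated widths 0.12 and 0.17, one-sided Fisher test at 0.025. Section 9.2.1.1: 775 enrolled, 562 basal-like. Section 9.5: subsets of 562, 158 and 35.

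**1. The plan's widths.** The exact (Clopper-Pearson) 95% limits for x events in n are the 0.025 quantile of Beta(x, n−x+1) and the 0.975 quantile of Beta(x+1, n−x). The width is maximised over x. The Wald maximum, at a rate of 0.5, is 2 × 1.96 × √(0.25/n).

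| n | Stated | Exact maximum | Wald maximum |
|---|---|---|---|
| 133 (per agent) | 0.17 | 0.1758 (at x=67) | 0.16995 |
| 267 (per arm) | 0.12 | 0.1231 (at x=134) | 0.1199 |

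At n=133 the stated 0.17 equals the Wald width. The exact width exceeds 0.17 for x=50 to 83, that is, observed rates of about 38% to 62%. An exact width of at most 0.17 at every rate needs n=142 per agent. At n=267 the exact maximum rounds to the stated 0.12.

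**2. The plan's power.** Full enumeration of the Fisher test with 267 per arm gives its lowest value, over the 13-point differences tried, at 43.5% versus 56.5%: 0.836. The claim of at least 83% is reproduced.

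**3. Share outside the main set.** With 775 enrolled: (775 − 562)/775 = 213/775 = 27.5%. The listed subsets sum to 562 + 158 + 35 = 755, which is 20 fewer; on that total the share is 193/755 = 25.6%. As shares of treated patients, both assume the same starting rate in every subtype.

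**4. All treated patients.** Assume that 95% start therapy, that the arms are equal, and that the platinum arm divides equally between agents, as Section 9.3.2 assumes.

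- Total 775: 775 × 0.95 / 2 ≈ 368 per arm; 368 / 2 = 184 per agent.
- Total 755: 755 × 0.95 / 2 ≈ 358 per arm; 358 / 2 = 179 per agent.

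| Set | Exact maximum, arm | Exact maximum, agent | Fisher power, 43.5% vs 56.5% |
|---|---|---|---|
| Basal-like (267 / 133) | 0.123 | 0.176 | 0.836 |
| All treated, 775 (368 / 184) | 0.105 | 0.149 | 0.935 |
| All treated, 755 (358 / 179) | 0.106 | 0.151 | 0.924 |

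**The case against.** The strongest reply is that Section 9.4 already plans an all-patient toxicity summary with a comparison between arms. This stands. A reader might infer from the basal-like restriction that about a quarter of treated patients are thrown away; the documents do not support that. Those patients are outside the main set but inside a planned addition, so most of the power gain shown for the arm comparison is already available there.

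It can also be said that leading with basal-like patients keeps toxicity in the population where non-inferiority is decided, and that if toxicity does not depend on subtype the basal-like estimate is not biased. Both are fair. The choice of lead set is then about precision and agreement with the objective, not validity.

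On patients with a failed assay, the governing phrase in the all-patient sentence is broad and its parenthesis need not be exhaustive. It would go too far to say that they are excluded; what can be said is that they are not expressly included.

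A reader might also take the per-arm 0.12 as a second error. It is not: 0.1231 is 0.12 to two decimals. The power statement is sound too. The per-agent slip is 0.006, matters only at mid-range rates, and drives no sample size, test or stopping rule. No toxicity result gates the efficacy conclusions.

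What the reply leaves open is the conflict in wording, the absence of any stated all-patient analysis or precision by agent, and the incorrect 0.17.

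**Conclusion.** The point holds as a mismatch between the safety population and its objective, plus one wrong precision figure. Treated basal-like patients, about 72.5% of the 775 planned (562/775), form the main toxicity set under a label that describes a larger one. The planned all-patient comparison reduces the consequence but does not settle where patients with unknown subtype belong or whether each agent is summarised in all patients.

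Making the all-treated set the main one narrows the maximum exact interval from 0.123 to about 0.105 per arm and from 0.176 to about 0.149 per agent. These figures assume 95% starting therapy among 775 and equal splits; with 755 they are 0.106 and 0.151. An unequal choice between cisplatin and carboplatin would change the per-agent widths under either set. The stated per-agent 0.17 should be 0.18 for the exact method at n=133. The effect is on clarity and precision of safety reporting; the efficacy design is untouched.

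**What to change.** In Sections 9.3.2 and 9.4, define the main safety set as all patients who took at least one dose, whatever the PAM50 result, naming basal-like, non-basal-like and unknown subtype. Report it by arm and by platinum agent, in line with objective 2.2.2, and keep the basal-like summary as a subset. Restate the maximum exact widths as about 0.105 per arm and 0.149 per agent, or 0.106 and 0.151 if 755 is the intended total, and give the assumptions beside them.

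If the sponsor prefers to keep basal-like as the main set, align objective 2.2.2 with it, drop the label that implies all treated patients, state that patients with unknown subtype are in the all-patient summary, say whether that summary is also given by agent, and change the per-agent width to 0.18. The per-arm 0.12 may stay.

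The cost is wording only. The study calendar in Section 7.1 schedules toxicity assessment in Arms B and C without regard to subtype, so no new data are needed.
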